9.1. Adverse Events

A treatment-emergent AE (TEAE) is defined as an AE that meets any of the following conditions:

- begins on or after the date of injection (Day 1);
- begins before the date of injection (Day 1) and worsens in severity on or after the date of injection (Day 1);
- is completely missing a start date and end date;
- is completely missing a start date and the end date is on or after the date of injection (Day 1).

For the purpose of inclusion in TEAE tables, incomplete AE start and end dates will be imputed as follows:

Missing onset dates (where UK and UKN indicate unknown or missing day and month respectively):

- UK-*MMM*-*YYYY*: If the month and year are different from the month and year of the date of injection, assume 01-*MMM*-*YYYY*. If the month and year are the same as the month and year for the date of injection, and the end date (after any imputation) is on or after the date of injection, then assume the date of injection (Day 1). If the month and year are the same as the date of injection, and the end date (after any imputation) is prior to the date of injection, then assume the end date for the start date.
- DD-*UKN*-*YYYY*/*UK*-*UKN*-*YYYY*: If the year is different from the year of the date of injection, assume 01-*JAN*-*YYYY* of the collected year. If the year is the same as the date of injection year, and the end date (after any imputation) is on or after the date of injection, then assume the date of injection (Day 1). If the year is the same as the date of injection, and the end date (after any imputation) is prior to the date of injection, then assume the end date for the start date.

Missing end dates (where UK and UKN indicate unknown or missing day and month respectively):

- UK-*MMM*-*YYYY*: Assume the last day of the month;
- DD-*UKN*-*YYYY*/*UK*-*UKN*-*YYYY*: Assume 31-*DEC*-*YYYY*.

All adverse events will be classified by System Organ Class and Preferred Term (PT) according to the Medical Dictionary for Regulatory Activities (MedDRA, Version 15.1 or higher).

An overview summary of the number and percentage of subjects with any TEAE, serious TEAE, treatment-related TEAE, treatment-related serious TEAE, TEAE leading to FAI insert removal, TEAE leading to study discontinuation, and AE leading to death will be provided by treatment group.

All AE summaries will be provided for ocular events and non-ocular events, separately. Ocular event tables will be presented by eye (study, fellow).

All AEs will be presented in a listing.

9.1.1. Incidence of Adverse Events

Summaries of the total number of TEAEs and the number and percentage of subjects with at least one TEAE will be provided by treatment group and overall. Treatment-emergent AEs will be presented by System Organ Class and PT. At each level of subject summarization, a subject is counted once if the subject reported one or more events. Percentages will be calculated out of the number of subjects in the Safety population.

The summary of TEAEs will be presented in descending order from the System Organ Class with the highest total incidence (that is, summed across all treatment groups) to the System Organ Class with the lowest total incidence. If the total incidence for any two or more System Organ Classes is equal, the System Organ Classes will be presented in alphabetical order. Within each System Organ Class, the PTs will be presented in alphabetical order.

A separate summary of protocol defined ocular AEs, overall and by criteria, will be provided. This summary will include the following ocular events, as reported on the AE eCRF page:

- decrease in visual acuity of at least ≥ 15 letters or ≥ 3 lines from the previous measurement of visual acuity
- moderate or severe (grade 3 or 4) ocular findings compared to the last ophthalmic examination
- worsening of ≥ 2 steps in anterior chamber cell count or vitreous haze, compared to the last ophthalmic examination
- increase in IOP of ≥ 10 mmHg at two visits at least 1 week apart or an increase in IOP to ≥ 25 mmHg

9.1.2. Relationship of Adverse Events to Study Treatment

A summary of TEAEs by relationship to study treatment will be presented in a table by incidence of occurrence. The investigator will provide an assessment of the relationship of the event to the study treatment. The possible relationships are “Unrelated”, “Possibly Related”, and “Probably Related”. In the TEAE relationship table, if a subject reports multiple occurrences of the same TEAE, only the most closely related occurrence will be presented. Treatment-emergent AEs that are missing a relationship will be presented in the summary table as “Probably Related” but will be presented in the data listing with a missing relationship. Percentages will be calculated based on the number of subjects in the Safety population.

The TEAE data will be categorized and presented by System Organ Class, PT, and relationship in a manner similar to that described in [Section 9.1.1](#).

9.1.3. Severity of Adverse Event

A summary of TEAEs by severity will be presented in a table. The severity that will be presented represents the most extreme severity captured on the eCRF page. The possible severities are “Mild,” “Moderate,” and “Severe.” In the TEAE severity table, if a subject reported multiple occurrences of the same TEAE, only the most severe will be presented. Treatment-emergent AEs that are missing severity will be presented in tables as “Severe” but will be presented in the data listing with a missing severity. Percentages will be calculated out of the number of subjects in the Safety population.

A summary of TEAEs related to study treatment by severity will be presented in a table. Events with a relationship of “Possibly Related” and “Probably Related” will be considered related to study treatment and included in this summary.

The TEAE data will be categorized and presented by System Organ Class, PT, and severity in a manner similar to that described in [Section 9.1.1](#).

9.1.4. Serious Adverse Events

Serious treatment-emergent adverse events (SAEs) will be presented in a table. Treatment-emergent SAEs by severity will be presented in a table. At each level of subject summarization, a subject is counted once if the subject reported one or more events. Percentages will be calculated out of the number of subjects in the Safety population.

The treatment-emergent SAE data will be categorized and presented by System Organ Class and PT in a manner similar to that described in [Section 9.1.1](#) and by severity as described in [Section 9.1.3](#).

A separate summary of protocol defined SAEs, overall and by criteria, will be provided. This summary will include the following sight-threatening ocular events, as reported on the AE/SAE eCRF page:

- An AE which causes a decrease in visual acuity of ≥ 30 letters or ≥ 6 lines from the most recent previous measurement of visual acuity, lasting more than 1 hour
- An AE which causes a decrease in visual acuity to light perception or worse, lasting more than 1 hour
- An AE which requires surgical intervention (e.g., conventional surgery, vitreous tap or biopsy with intravitreal injection of anti-infectives, or laser or retinal cryopexy with gas) to prevent permanent loss of sight
- An AE which is associated with severe intraocular inflammation (i.e., 4.0 anterior chamber cell score, 4+ flare or 4+ vitritis)
- Two consecutive IOP measurements of 30 mmHg or higher taken at least 72 hours apart when a subject is already being treated with two glaucoma medications
- An IOP < 6 mmHg requiring medical intervention

- An AE which in the opinion of the investigator requires medical or surgical intervention to prevent permanent loss of sight

9.1.5. Adverse Events Leading to FAI Insert Removal

A summary of TEAEs with an action taken with study treatment of “FAI Insert Removal” will be presented in a table. At each level of subject summarization, a subject is counted once if the subject reported one or more events. Percentages will be calculated out of the number of FAI insert subjects in the Safety population.

The summary of TEAEs with an action taken with study treatment of “FAI Insert Removal” will be presented in descending order of frequency from the System Organ Class with the highest total incidence (that is, summed across all treatment groups) to the System Organ Class with the lowest total incidence. Within each System Organ Class, the PTs will be presented in alphabetical order.

9.1.6. Adverse Events Leading to Study Discontinuation

All subjects who have an AE where the answer to “Was Subject Terminated from study due to this AE?” is “Yes” will be presented in a listing.

9.1.7. Death

All subjects who have an AE with an outcome of “Fatal” will be presented in a listing.

9.1.8. Adverse Events of Special Interest

A summary of TEAEs of cataract and elevated IOP will be presented in a table by treatment group and overall. Events will be included in the summary based on a list of preferred terms for each event category. At each level of subject summarization, a subject is counted once if the subject reported one or more events. Percentages will be calculated out of the number of subjects in the Safety population. Within each event category, the PTs will be presented in alphabetical order.

A summary of ocular TEAEs which are considered complications of IOP lowering medications to control IOP will be presented by treatment group and overall. Events will be included in the summary based on a list of preferred terms and an onset date on or after the date of first use of any IOP lowering medication. The list of PTs will be generated based on the most common adverse events associated with the IOP lowering medications used.

A summary of ocular TEAEs which are considered complications of surgical interventions to control IOP will be presented by treatment group and overall. Events will be included in the summary based on a list of preferred terms and an onset date on or after the date of surgical intervention. A similar summary will be presented for complications of cataract surgeries.

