A higher incidence of anemia (irrespective of relationship to drug) was observed in subjects who received Iluvien compared to sham (3%, sham; 7%, 0.2 μg FA /day; 9%, 0.5 μg FA /day). The cause of this increase is not known and was not considered by the Data Monitoring Safety Board to be related to FA. It has been hypothesized that the increase may be due to the use of oral carbonic anhydrase inhibitors (CAIs) (which occurred more frequently in the active treatment groups). This class of IOP-lowering drugs is known to exacerbate renal dysfunction and possibly compromise erythropoietin production. A post-hoc analysis was performed in which all subjects were categorized with or without anemia and with or without a systemic CAI (administered during or within 90 days of anemia). Based on a Pearson chi-square test, there was a relationship between the use of a CAI and anemia in the 0.2 μg FA /day group (p-value <0.0001, and in the 0.5 μg FA /day group (p=0.0073).

Deaths and Serious Adverse Events

A total of 56 (6%) deaths were reported in the FAME studies. None of the deaths were attributed to study drug or unexpected in the patient population.

A total of 401 (42%) subjects had at least 1 drug-related serious adverse event (SAE), all of which were ocular in nature. The overall incidence of drug-related SAEs was several-fold higher in the Iluvien insert groups relative to sham.

Ocular Adverse Events

In the FAME Studies, the most common drug-related TEAEs were cataract operation (39% of subjects), cataract (36%), increased intraocular pressure (25%), and myodesopsia (8%).

Cataract-Related Events in Phakic Subjects

The FAME studies enrolled 621 subjects with phakic study eyes at baseline; the remaining 335 study eyes were pseudophakic at baseline. The incidence of cataract in the study eye was higher in the active treatment groups [80% (low dose), 88% (high dose)] than in the sham group (46%). The most common types of cataracts in the study eye were cataract (NOS) and posterior subcapsular cataract, both of which were reported more frequently in the active treatment groups than in the sham group. The percentage of phakic subjects who had a cataract operation in the study eye was also higher in the active treatment groups [75% (low dose), 85% (high dose)] than in the sham group (23%).

IOP-Related Events and Procedures

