9.10.4. Cataract Removal and Other Elective Ocular Surgery

Cataracts are recommended to be removed by extra-capsular extraction with phacoemulsification. A cataract may be removed prior to a subject's enrollment.

Because of the importance of VA evaluations in this study, the timing of cataract removal or any elective surgery during the post-treatment follow-up period should be scheduled at least 4 weeks prior to any study visit involving VA assessment.

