3.2. Study Endpoints

The primary efficacy endpoint is the proportion of subjects who have a recurrence of uveitis in the study eye within 6 months after receiving study treatment. Recurrence is captured on the Recurrence of Uveitis eCRF page and, for the US/FDA, is defined as:

- An increase in the vitreous haze of ≥ 2 steps, compared to baseline or any visit time point prior to Month 6
OR
- A deterioration in visual acuity of at least 15 letters BCVA, compared to baseline or any visit time point prior to Month 6

Any criterion used to define recurrence must be attributable only to noninfectious uveitis. To prevent post-procedural inflammatory reactions from being reported as uveitis recurrences, assessments for recurrence of uveitis begin after the study Day 7 visit.

The exploratory efficacy endpoints include:

- Proportion of subjects who have a recurrence of uveitis in the study eye within 12 months and 36 months
- Proportion of subjects who have a recurrence of uveitis in the fellow eye (within 6 months, 12 months and 36 months)
- Mean change from baseline in best-corrected visual acuity (BCVA) letter score in the study eye (at 6 months, 12 months and 36 months)
- Number of recurrences of uveitis (within 6 months, 12 months and 36 months)
- Time to recurrence of uveitis in the study eye (within 6 months, 12 months and 36 months)
- Number of adjunctive treatments required to treat recurrences of uveitis (within 6 months, 12 months and 36 months)
- Resolution of macular edema, as measure by OCT imaging (at 6 months, 12 months and 36 months)

In addition, the following safety endpoints will be included in the analysis:

- Systemic adverse events
- Ocular adverse events, including intra-ocular pressure (IOP) elevation
- Medications/procedures required to control elevated IOP
- Development or worsening of cataract
- Cataract-related procedures
- Clinically significant ocular changes
- Treatment related adverse events

4. General Statistical Considerations

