Only those assessments which are assigned to an analysis visit will be included in the summary tables and figures which are presented by visit. For summaries of an event at or before a given time point, such as recurrence at Month 12, all assessments (including unscheduled visits) on or before the upper limit of the corresponding visit window will be considered. All assessments will be presented in the data listings.

For summaries presented by 3 month time intervals through Month 12, the intervals will be defined based on study days and the analysis visit windows, as follows:

- Day 1 to 3 months: day 1 to day 97 (upper limit of Month 3 visit window)
- 3 to 6 months: day 98 to day 208 (upper limit of Month 6 visit window)
- 6 to 9 months: day 209 to day 298 (upper limit of Month 9 visit window)
- 9 to 12 months: day 299 to day 388 (upper limit of Month 12 visit window)

For summaries presented by 6 month time intervals, the intervals will be defined based on study days and the analysis visit windows, as follows:

- Day 1 to 6 months: day 1 to day 208 (upper limit of Month 6 visit window)
- 6 to 12 months: day 209 to day 388 (upper limit of Month 12 visit window)

- 12 to 18 months: day 389 to day 568 (upper limit of Month 18 visit window)
- 18 to 24 months: day 569 to day 748 (upper limit of Month 24 visit window)
- 24 to 30 months: day 749 to day 928 (upper limit of Month 30 visit window)
- 30 to 36 months: day 929 to day 1108 (upper limit of Month 36 visit window)

The Month 6 analysis will include all assessments (events, medications, etc.) with a start day on or before the upper limit of the Month 6 visit window (study day 208). The Month 12 analysis will include all assessments (events, medications, etc.) with a start day on or before the upper limit of the Month 12 visit window (study day 388). The analysis at Month 36 will include all data in the database.

For tabulations of data on the Safety population, subjects who were randomized but did not receive treatment will not be included; however data for all subjects in the Safety population will be included in the data listings. In the listings, subjects who did not receive treatment will be grouped separately by their randomized treatment assignment (i.e., FAI Insert - Not Treated, Sham Injection - Not Treated). Percentages for Safety population summaries will be based on the total number of subjects who receive treatment.

All analyses will be conducted using SAS Version 9.2 or higher.

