4.3.3. Safety

The Safety population will include all randomized subjects. All subjects in the Safety population will be analyzed according to the treatment actually received and not according to the treatment they were randomized to receive, in the event there is a discrepancy. Similarly, in any Safety analysis by systemic treatment at study entry (randomization stratification factor), subjects will be analyzed by the actual strata to which they belong and not according to the strata under which they were randomized, in the event there is a discrepancy.

5. Subject Disposition

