6.2. Baseline Disease and Ocular Characteristics

A summary of baseline disease characteristics will be presented for the study eye and fellow eye for the ITT and Safety populations. Summaries will be generated for the Safety population only if there are randomized subjects who do not receive treatment. The baseline characteristics consist of study eye, randomization strata for systemic treatment to control uveitis, duration of uveitis (years), number of recurrences in the last 12 months, lens status, presence of cataract, history of vitrectomy procedure and history of incisional surgery to control elevated IOP.

Duration of uveitis is calculated as (Screening date – date of onset of uveitis +1)/ 365.25 and will be summarized using descriptive statistics. For partial onset dates, a missing month will be imputed as January and a missing day will be imputed as the first of the month.

The number and percentage of subjects by study eye (OD, OS), randomization strata (Not receiving systemic treatment, Receiving systemic treatment – corticosteroid therapy, Receiving systemic treatment – immunosuppressive therapy), duration of uveitis (< 2 years, 2 to 5 years, > 5 years), number or recurrences (<= 2, >2), lens status (phakic, aphakic, and pseudophakic), presence of cataract for subjects with a lens status of phakic, history of vitrectomy procedure, and history of incisional surgery to control elevated IOP will also be reported. Percentages will be based on the total number of subjects in the ITT or Safety population, as applicable.

In addition, baseline ocular characteristics will be summarized for the study eye. The baseline ocular characteristics consist of severity of macular edema, IOP (mmHg), and BCVA (letters). Baseline IOP and BCVA will be summarized using descriptive statistics. The number and percentage of subjects by baseline severity of macular edema (CSFT < 300 microns, CSFT >= 300 microns) will also be reported.

Subject baseline disease and ocular characteristics will be presented in a listing.

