7.2.2 Cataract Surgeries

The number and percentage of subjects requiring cataract surgery will be summarized by treatment group, eye (study, fellow), and time interval. Only eyes which are indicated as phakic at study entry will be included for analysis. Ocular surgeries with a reason of “Cataract” will be included in the summary. Incidence will be summarized overall through 6 months and for 6 month time intervals through 12 (or 36) months. All summaries will be performed using the Safety population and percentages will be based on the total number of phakic eyes in the Safety population.

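### SAP 9.1.8 puts cataract adverse events over all treated subjects, which understates absolute incidence and the FAI–sham difference for eyes still at risk

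*SAP*

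**What the plan says.** SAP 3.2 lists "Development or worsening of cataract" among the safety endpoints. SAP 9.1.8 then summarises treatment-emergent cataract and elevated IOP events in one table, with this base: "Percentages will be calculated out of the number of subjects in the Safety population. Within each event category" (the quotation runs into the next sentence, on the order of terms). On who is counted, SAP 4.3.3 says "The Safety population will include all randomized subjects", and SAP Section 4 (General Statistical Considerations) adds: "Percentages for Safety population summaries will be based on the total number of subjects who receive treatment". SAP 9.1 splits ocular event tables into study and fellow eye. None of these rules mentions lens status.

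Eyes without a natural lens are expected. SAP 6.2 tabulates "lens status (phakic, aphakic, and pseudophakic), presence of cataract for subjects with a lens status of phakic", SAP 8.1.4 uses the same three lens categories as subgroups, and Protocol 9.10.4 allows a cataract to be removed before enrolment. SAP 4.2 stratifies randomisation on systemic treatment only.

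Two other cataract analyses do handle lens status. For surgery, SAP 7.2.2 includes only eyes phakic at study entry, and "percentages will be based on the total number of phakic eyes in the Safety population". SAP 9.2.4 presents slit-lamp change in lens or cataract status by baseline lens status.

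**The concern.** An eye whose lens has already been removed cannot develop or worsen a cataract, yet it sits in the denominator of the cataract adverse event rate. The percentage in 9.1.8 is therefore a mixture of the risk in phakic eyes and the proportion of eyes that happen to be phakic. Cataract is one of only two event categories that the SAP singles out by name, and a phakic patient wants the rate among phakic eyes. Within one report, the cataract event table and the cataract surgery table would use different bases, so their percentages could not be set side by side. With 80 and 40 subjects and no stratification on lens status, the displayed difference between arms would also carry noise that has nothing to do with the insert.

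**Working it through.** The documents state no expected cataract incidence for this trial, so there is no such figure to reproduce. The one stated design figure, 89% power, has no bearing on this point, but it does reproduce. With 40 sham subjects, a 2:1 ratio and a difference of 0.88 − 0.60 = 0.28, the continuity-corrected effective sham size is 40 × [1 − 3/(2 × 2 × 40 × 0.28)]² = 34.8, which gives 89.2%.

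**Inputs (illustrative, from Protocol 5.3.2.2.2).** The earlier studies of the near-identical insert were 36-month studies in diabetic macular edema. On lens status: "The FAME studies enrolled 621 subjects with phakic study eyes at baseline; the remaining 335 study eyes were pseudophakic at baseline". The phakic share is therefore 621/(621 + 335) = 621/956 = 65.0%. Under the heading for phakic subjects, cataract incidence was 80% on the low dose and 46% on sham. Arm sizes of 80 and 40 are from SAP 4.1.

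**Step 1, dilution.** If non-phakic eyes have no cataract events, the displayed rate is the phakic share multiplied by the rate in phakic eyes.

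| Phakic share | FAI | Sham | Displayed excess |
|---|---|---|---|
| 100% (phakic eyes only) | 80% | 46% | 34 points |
| 80% (assumed) | 64.0% | 36.8% | 27.2 points |
| 65.0% (DME studies) | 52.0% | 29.9% | 22.1 points |
| 40% (assumed) | 32.0% | 18.4% | 13.6 points |

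**Step 2, risk ratio.** 80/46 = 1.74 and 52.0/29.9 = 1.74. With equal phakic shares in the two arms, the share cancels.

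**Step 3, chance imbalance.** At a 65% share, the standard deviation of the between-arm difference in phakic share is √[0.65 × 0.35 × (1/80 + 1/40)] = 0.092, or 9.2 points. By exact binomial enumeration, the probability of an imbalance of 10 points or more in either direction is about 31% (23% to 33% for shares from 40% to 80%). Take a 10-point imbalance with the overall share held at 65%:

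- FAI 61.6% phakic, sham 71.6%: 0.80 × 61.6 = 49.3%, 0.46 × 71.6 = 32.9%. Excess 16.4 points, risk ratio 1.50.
- FAI 68.3% phakic, sham 58.3%: 0.80 × 68.3 = 54.6%, 0.46 × 58.3 = 26.8%. Excess 27.8 points, risk ratio 2.04.

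From lens balance alone, the central 95% range of the displayed excess at a 65% share is about 11 to 33 points. The risk in phakic eyes is the same throughout.

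**The case against.** The strongest reply is that one descriptive table is affected, and the rest of the plan covers the risk.

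- SAP 9.2.4 is the analysis closest in wording to the cataract endpoint, and it is split by baseline lens status. SAP 7.2.2 gives surgery rates among phakic eyes. This stands, but neither table gives adverse event incidence: the first is examination data and the second counts only operated cataracts.
- SAP 6.2 tabulates lens status for both eyes, and Protocol 14.3.1 has baseline tables by treatment group. A reader could divide the event count by the phakic count and see any imbalance. This largely stands, provided the preferred terms cannot occur in non-phakic eyes. It asks the reader to do a calculation that the table should show.
- Protocol 5.3.2.2.2 also quotes all-subject figures for drug-related events (cataract operation 39%, cataract 36%), so an all-subject table has a precedent. This stands, though those figures pool the arms and cover only drug-related events; the cataract rates given by arm are under the phakic heading.
- Simply replacing the denominator would make 9.1.8 disagree with the general event tables in SAP 9.1.1 for the same terms. The term list for 9.1.8 is not given, and a phakic-only table could drop lens or capsule events in pseudophakic eyes. This stands, and it argues for adding a table and keeping the current one.

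**Conclusion.** The point holds for the cataract percentages in SAP 9.1.8. As written, they understate the absolute incidence and the risk difference for eyes that can develop a cataract, and they move in either direction with chance lens balance. It is a worthwhile correction to a safety table; no test or decision rule depends on it.

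A reader might infer that the plan as a whole conceals or understates cataract risk, that relative harm is diluted, or that chance imbalance always favours the insert. The documents support none of these. At-risk summaries of surgery and slit-lamp findings are planned, the risk ratio is unchanged when lens status is balanced, and imbalance can raise the displayed excess as easily as lower it.

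The size is illustrative. This trial's phakic share and cataract rates are not in the documents; the 65%, 80% and 46% come from a diabetic population over 36 months, and the 40% to 80% range is an assumption. The arithmetic also assumes no listed event in non-phakic eyes; if the term list includes events possible in pseudophakic eyes, the dilution is smaller.

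**What to change.** Add to SAP 9.1.8 a summary of treatment-emergent cataract events by treatment group and by eye (study, fellow), restricted to eyes phakic at study entry and using the denominator of SAP 7.2.2. Name it as the main cataract adverse event incidence. Keep the Safety-population table as secondary, so that it agrees with the general tables in 9.1.1, and keep that denominator for elevated IOP. State which preferred terms enter the cataract category.

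The cost is one extra table from lens status already collected, and a higher displayed cataract rate. SAP 11.2 already records changes made after unmasking, and this addition should be logged there with its reason: it uses only a baseline variable and a rule that the SAP already applies to surgery.
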